Ten (10) stable patients receiving regular dialysis treatment will be chosen for this evaluation. The n of ten was chosen from previous experience with studies of this kind. However with the expectation of a 20% drop out rate a total of twelve patients will be selected from the patient population meeting the inclusion criteria. Standard hemodialysis will be performed with each dialyzer type.

d) Patient Inclusion Criteria

- ESRD patients 18 years or older
- Stable on hemodialysis for more than 3 months
- Stable hemoglobin 11 g/dl or greater, see attached DCI erythropoietin protocol.
- Stable AV fistula vascular access
- Stable anticoagulation and ESA regimen

- No active infection
- Able to sign informed consent and able to participate in the study
- Medically stable

e) Patient Exclusion Criteria

- Participation in another study which may interfere with the planned study
- Active infection
- Medical conditions which may interfere with the study (cardiac, liver disease,
- Hepatitis)
- Female who are pregnant or planning to be pregnant
- Problem with or allergy to anticoagulation
- Patient cannot tolerate Heparin
- Allergy to dialyzer material e.g. polysulfone

f) Withdrawal Criteria

- Patients own decision.
- Relocation, transportation
- Severe mechanical problems with dialyzers e.g. frequent fiber leakages.
- Hypertensive reactions e.g. erythema, edema.
- Non-compliance with therapeutic regimen.
- Change of anticoagulation scheme.
- Other serious problems induced by treatment.
- Any dialysis-related medical problem judged to be sufficiently serious by the principal investigator to necessitate patient withdrawal.

1. Methods

a) Pre-rinsing of Dialyzers

Setting up and preparation of the dialyzers will be performed per the clinic's normal procedure. This involves a pre-rinsing step before the start of dialysis.. The priming solution will not be infused to the patient. Dialysate flow rate is to be initiated at the beginning of the rinsing procedure. All the dialyzers will be pre-rinsed in the same procedure.

b) Heparinization

The usual heparin type and dosage normally used for each individual patient, including the administration regime (bolus injection and continuous infusion), will be maintained

for each patient unless specified otherwise by the investigator/physician during the evaluation. The total amount of heparin given per treatment will be documented.

c) Blood Flow / Dialysate Flow

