Hemodialysis: Blood and dialysate flow rates should be between QB= 300 - 500 ml/min and QD= 2 times QB but should follow existing flow rates for the patient, based on clinic procedure. Blood flow and dialysate flow should remain unchanged for all patients for the duration of dialysis and throughout the evaluation. The ultrafiltration rate, appropriate for each patient and treatment will be maintained and recorded. The blood flow will also be determined in the fistula using a Doppler flow device.

d) Dialysis Regime and Number of Applied Dialyzers

Three consecutive treatments will be performed with each dialyzer type. Blood sampling for measurements will be taken as shown in appendix.

e) Performance and Hemocompatibility Parameters to be measured

Please refer to Appendix.

f) Blood Sampling

Blood will be collected pre-, during and post-dialysis at appropriate time intervals (see Appendix) for the evaluation of:

- Clearance of urea, creatinine, phosphate, beta-2-microglobulin, myoglobin at 60 min. Five minutes before the collection the flow rate will be adjusted so that at time of collection, QB= 350 mL/min, QD= 700 mL/min and UF= 0 for all patients. Blood is to be collected from venous side first followed by arterial side.
- 2. **Removal Rate** for urea, creatinine, phosphate, beta-2-m and myoglobin at 0 min and 240 min will be calculated.

3. Hemocompatibility

- (a) Blood cell count (white blood cell and platelet counts).
- (b) Hb / Hct.
- (c) C5a (activation of complement)
- (d) Thrombin-Antithrombin Complex (TAT)

The samples will be collected after confirming that the blood and dialysate flows are at the targeted rates listed above, venous and arterial pressure at point of collection are to be recorded as well. For blood volumes see appendix B.

g) Visual estimation of the amount of clotted capillaries

After dialysis removal of the residual blood is performed by means of ultrafiltration with reverse osmosis water from dialysate compartment to blood compartment (0.5-1 bar water pressure and the overall appearance of dialyzer will be photographed, with focus on the clotted fibers and any residual header blood. This will be carried out at the end of each treatment for each dialyzer (3 times each dialyzer). The number of clotted capillaries in the dialyzer are counted after removal of the plastic casing and classified by the following table.

	Number of clotted fibers							
	0 – 10 11 – 20 21 – 50 51 – 100 >100							
Score	1	2	3	4	5			

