Statistical Analysis Plan

For

A Clinical Study Comparing the Basic Performance and Blood Compatibility Characteristics of Nipro ELISIO-H, Gambro Polyflux Revaclear and Fresenius Optiflux Dialyzers

NCT02433210

July 23, 2019

Software:

Data were analyzed in house using SigmaPlot for Windows 11.2 (Systat Software, Inc., San Jose, CA, USA) for statistical analysis.

Methods:

Parametric non-paired t-test was used to compare groups except where the data failed the normality test or the variance test, then the nonparametric Mann–Whitney Rank Sum was utilized to test for significance.

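### The SAP lets a pre-test on the same data choose between an unpaired t-test and Mann-Whitney, so the hypothesis can change between dialyzer pairs, and both branches ignore the within-patient design

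*SAP*

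**What the plan says.** The Methods paragraph of the SAP is one sentence. The default is stated as "Parametric non-paired t-test was used to compare groups", which applies "except where the data failed the normality test or the variance test"; in that event "then the nonparametric Mann–Whitney Rank Sum was utilized to test for significance". Because the two triggers are joined by an or, a failed variance test is enough by itself to move a comparison to Mann-Whitney.

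The SAP does not name the two pre-tests, their cut-offs, the significance level, the parameter being compared or an effect measure. It has no rule that one outcome keeps one method. The protocol has no analysis section that fills these gaps.

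On design, section c) Patients of the protocol says "Standard hemodialysis will be performed with each dialyzer type", and section 1.d says "Three consecutive treatments will be performed with each dialyzer type". Appendix A schedules clearance and removal-rate samples three times per dialyzer for each patient, and hemocompatibility samples once per dialyzer for each patient. Appendix B budgets three weeks of blood per patient: 131.5 ml × 3 = 394.5 ml. Each patient is therefore measured on all three dialyzers.

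**The concern.** Two things are wrong with the rule.

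First, the switch does not suit one of its own triggers. The t-test concerns a difference in means. Mann-Whitney concerns P(X<Y), and it can be read as a comparison of location only if the two distributions share shape and spread. A failed variance test is evidence that they do not. The data thus decide which question is asked, separately for each outcome, time point and dialyzer pair. At about ten values per group the pre-tests are a weak basis for that decision. The results cannot be lined up across the three dialyzers, and no single effect measure is specified in advance.

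Second, both branches treat the same patients as two independent groups. This misstates the standard error whichever way the gate falls.

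At stake is whether the comparisons of performance and hemocompatibility give interpretable and reasonably precise differences from a study of this size.

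**Working it through.** **Inputs from the documents.** Ten evaluable patients, justified only by "The n of ten was chosen from previous experience with studies of this kind". Three dialyzers per patient. Unpaired t-test or Mann-Whitney, chosen by pre-test. The only sample-size figure that can be recomputed is the number selected: 10 × 1.20 = 12, as stated (10 / 0.80 = 12.5 would round up to 13). Nothing below depends on it.

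**Assumptions, because the documents give none.** Two-sided 5% level; Shapiro-Wilk on residuals and median-based Levene as the pre-tests, each at 5%; SD ratios 1 to 4; within-patient correlation ρ of 0.5 to 0.6; log-normal markers as specified below.

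**Step 1: the two branches test different hypotheses.** Take two log-normal distributions with log SDs 0.3 and 0.8.
- Equal means: set the log means to −0.3²/2 = −0.045 and −0.8²/2 = −0.32. Then P(X<Y) = Φ[(−0.32 + 0.045) / √(0.3² + 0.8²)] = Φ(−0.275 / 0.854) = 0.37. The t-test's null is true and the Mann-Whitney null is false.
- Equal medians: P(X<Y) = 0.5, but the means differ by a factor exp(0.275) = 1.32. Now the t-test's null is false.

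**Step 2: how often the gate diverts.** For a log-normal marker with log SD 0.5, ρ = 0.6 and a true ratio of 1.6 at n = 10, simulation sends 50% to 51% of comparisons to Mann-Whitney. With three dialyzers, the three pairwise comparisons of one marker do not all use the same test in 46% to 51% of simulated trials. Even with normal data and equal SDs, about 9% of comparisons are diverted.

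**Step 3: null rejection rate under the actual design.** With SDs r and 1, the unpaired formula takes the variance of the mean difference as (r² + 1)/n. The true value is (r² + 1 − 2ρr)/n. The standard error is overstated by √[(r² + 1)/(r² + 1 − 2ρr)]:

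| SD ratio r | ρ = 0.5 | ρ = 0.6 |
|---|---|---|
| 1 | √(2/1) = 1.41 | √(2/0.8) = 1.58 |
| 3 | √(10/7) = 1.20 | √(10/6.4) = 1.25 |
| 4 | √(17/13) = 1.14 | √(17/12.2) = 1.18 |

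In simulation (normal data, equal means, n = 10) the gated procedure rejects about 1% or less at SD ratio 1 and 2.7% to 4.5% at ratios 3 to 4. A paired t-test on the same kind of data holds 4.9% to 5.2% for SD ratios 1 to 5 and correlations 0 to 0.7.

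**Step 4: power, and where the gap comes from.** In the log-normal case of step 2, the log difference is ln 1.6 = 0.470.
- Paired on logs: SE = 0.5 × √(2 × 0.4/10) = 0.141, so the difference is 0.470/0.141 = 3.3 SEs on 9 df.
- Unpaired on logs: the formula uses SE = 0.5 × √(2/10) = 0.224, giving 0.470/0.224 = 2.1 SEs on 18 df.

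Simulated power:

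| Analysis | Power |
|---|---|
| SAP gate, raw values | 50% |
| Unpaired Welch, raw values | 45% |
| Unpaired t-test on logs | 54% |
| Paired t-test on logs | 85% |

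The total gap is 85 − 50 = 35 points. Of this, 85 − 54 = 31 points come from pairing. Removing the gate and taking logs, while staying unpaired, gains 54 − 50 = 4 points.

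**The case against.** A reader might infer that the rule inflates the type I error, since Mann-Whitney is known to exceed its nominal level under unequal spread. For independent groups of ten at SD ratios 3 to 4, the gated procedure does reject 6.2% to 7.1% of the time. The documents do not support applying those figures here: the groups are the same patients, and any plausible positive correlation pulls the rate below 5% for roughly symmetric outcomes. Nor do the documents show that SD ratios of 3 to 4 occur between three dialyzers of similar surface area (1.4 to 1.6 m²). That objection stands, and inflation is not part of this point.

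It has one limit. With strong skew and unequal log SDs (0.3 v 0.8), equal means, n = 10 and ρ = 0.5, Mann-Whitney rejects 12.6%. This is not a case for a raw-scale t-test, because the paired t-test on raw values gives 11.5% in the same setting. It shows instead that the scale and the estimand must be chosen beforehand.

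Three further objections hold in part.
- Mann-Whitney is not invalid as such: it keeps its level for independent samples under the null of identical distributions. The complaint is about reading it as a comparison of means or medians.
- An effect measure can be attached to each test, a mean difference to one and a Hodges-Lehmann shift to the other. The fair complaint is that none is specified and that the two are not the same quantity.
- The diversion rate of about one half rests on one assumed log-normal shape and will differ for other markers.

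None of these gives the comparisons a consistent hypothesis.

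**Conclusion.** The point holds as a defect of hypothesis and design. The gate can put the same marker on means for one dialyzer pair and on ranks for another, and a variance failure triggers a test that does not address unequal variance. Both branches discard the within-patient pairing.

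The pairing loss has the larger numerical effect. For normal data the procedure is conservative (about 1% or less at equal SDs, 2.7% to 4.5% at SD ratios 3 to 4), and power is about 50% against about 85% in the log-normal case. It would be a misreading to charge that 35-point gap to the choice of Mann-Whitney, since about 31 points of it come from ignoring pairing. The gate's own harm is the mixed hypothesis and the lack of a common estimate.

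All rates rest on assumed SDs, correlations, significance level and pre-tests. That the hypothesis depends on the data, and that pairing is ignored, follows from the documents alone.

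**What to change.** Delete the pre-test rule and name one within-patient method per outcome:
- Clearance and removal rate: paired differences between dialyzers, averaging the three treatments per dialyzer within each patient, or a mixed model with a patient effect. State which.
- C5a and TAT: paired differences of log values, back-transformed and reported as ratios with confidence intervals.
- Signed-rank test as a sensitivity check only.

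State the significance level and the effect measure for each outcome. Do not replace Mann-Whitney with an unpaired Welch test. It would leave the pairing error in place, and in the log-normal case its power on raw values (45%) is below that of the present rule.

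The cost is a few lines of SAP text and a short re-run on existing data, with no new sampling. Because the SAP, dated July 2019, describes the analysis in the past tense, the re-run should be labelled a reanalysis and reported alongside the original results.
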